**NCT06156969**

**MAY 3RD, 2019**

## DATA ANALYSIS PLAN

Descriptive statistics will be derived for the primary and secondary outcome measures used in the study. Outcome measure values will be compared pre- vs post-intervention to assess changes associated with robot-assisted training. Cosine similarity values will be derived by comparing the composition of the muscle synergies pre- and post-intervention with normative synergies. The difference between post- and pre-intervention cosine similarity values will be measured as percentage of the scale (0-1 value). Data for the Gross Motor Function Measure scale section D and E will be compared pre- vs post-intervention, and the difference will be measured as percentage of the scale range (i.e. 39 points for the section D score and 72 points for the section E score). Finally for the 10-meter walk test, the 6-minute walk test and the Edinburgh Visual Gait Score scale, we will estimate the improvement in clinical outcome measure and derive the percentage improvement relative to the baseline value. For each of these outcome measures, we will estimate mean and standard deviation values of the improvement in clinical score for each outcome measure as explained above.

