Previous studies have shown the sensitive nature of EMG to represent an aberrant motor control in CP¹¹. Children with CP utilize fewer synergies during gait than typically developing children. The complexity of control, as measured by synergies, is reduced during gait in individuals with CP compared with unimpaired individuals and is related to functional ability and clinical measures.

The similarity of synergies in CP, stroke, and infant rhythmic-stepping indicates that there are common changes in control after brain injury that may reflect control in early development¹².

Training interventions to improve gait outcomes in CP usually include strength training, balance control and weight bearing activities¹³. Some studies have demonstrated beneficial effects of intensive task-specific gait training on motor recovery in children with CP^{14,15}.

Robotics has been looked upon as a means to achieve intensity and specificity of gait training, which are known to be key “ingredients” needed to maximize motor gains^{16,17}. The most prominent device used to deliver gait training is the Lokomat system (Hocoma AG, Switzerland) shown in *Figure 1*. The system is a driven (i.e., motorized) gait orthosis (DGO), namely a computer-controlled exoskeleton that is secured to a person’s lower limbs while he/she walks on a motorized treadmill

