A convenience sample of 30 children with CP with no major orthopedic or neurological complications that could interfere with the gait-training program will be recruited in the study. A study clinician will screen potential subjects. Screening will include a standard history and physical exam to ensure subjects meet all entry requirements after consideration of inclusion and exclusion criteria.

Inclusion criteria:

- Diagnosis of spastic CP
- 6 to 18 years of age.
- Gross Motor Function (GMFCS) Level I, II, III or IV.
- Body/femoral length < size of Lokomat robotic arm (femur length between 210-350mm)
- Ability to communicate pain or discomfort.

Exclusion Criteria:

- Recent use of Lokomat within the last 3 months.
- Contraindication to robot-assisted gait training such as thromboembolic disease, progressive neurologic disorder, cardiovascular or pulmonary contraindications, aggressive behaviors, severe cognitive deficits, bone instabilities, fractures, osteoporosis).
- Skin ulcers in trunk or lower limbs.
- Hip, knee, ankle arthrodesis.

Briefly describe study procedures. Include any local site restrictions, for example, “Subjects enrolled at Partners will not participate in the pharmacokinetic portion of the study.” Describe study endpoints.

All study procedures will take place in the Motion Analysis Laboratory at Spaulding Rehabilitation Hospital, Boston, Massachusetts, USA. Spaulding Rehabilitation Hospital is an affiliated hospital of Harvard Medical School.

Assessments

Assessments will be performed before and after the study participant undergoes robot-assisted gait therapy. Each assessment will require approximately 4-hours. The majority of this time will be spent sitting down, attaching markers and electrodes on the subject, checking the position of the markers and sensors, and measuring lengths of body segments. But we will give the option to the families of dividing the assessments into two different appointments.

Visit 1: Clinical tests

Clinical tests will be conducted by a study staff to assess lower limb function before and after the intervention. Throughout the study visit (notably during the clinical testing) if subjects feel tired, they will be given every opportunity to rest; this, in addition to regular rest breaks between the test trials. Clinical tests will include:

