Gait evaluations will be performed in the Motion Analysis Laboratory before and after robot-assisted gait training. Subjects will be asked to change into shorts and shirt. Measurements of the knee and ankle joint and leg lengths will be taken before testing. Surface electromyographic (SEMG) data will be gathered to study the characteristics of muscle activation patterns in children with cerebral palsy during the gait. Data will be collected using electrodes for the detection of EMG activity from muscles that are involved in the gait. Simultaneous recordings of movement patterns will be performed using a camera-based system for motion analysis. Movements of the upper limbs, trunk and lower limbs, will be tracked using a standard set of reflective markers positioned on anatomical landmarks such as acromioclavicular joint, upper arm, lateral epicondyle, forearm, wrist, 7th cervical vertebrae, 10th thoracic vertebrae, clavicle, sternum, the sacrum, anterior superior iliac spine, lateral thigh, distal lateral epicondyles, lateral shank, lateral malleolus, center of calcaneus and second metatarsal head. We will follow the SENIAM (Surface Electromyography for the Non-Invasive Assessment of Muscles) guidelines to place up to 16 electrodes on several muscles involved in the gait pattern, including the following: Gastrocnemius, Soleus, Tibialis Anterior, Peroneus longus, Rectus Femoris, Vastus Medialis and Lateralis, Sartorius, Biceps Femoris, Semitendinosus, Adductor Longus, Tensor Fascia Latae, Gluteus Maximus and Gluteus Medium, Obliquus and erector spinal muscles. The EMG will be attached using bio-adhesive double sided tape and secured with Coban. Each subject will be asked to do this several times until about 5-10 trials with good foot contacts onto the force plates are collected for each side (leg) of the body. Subjects will be asked to complete 5-10 trials walking barefoot (if possible), and then 5-10 trials walking in their shoes with any brace(s) they may normally wear. Rest breaks will be given during the testing. We will ask permission to study participants to video record them during the performance of the above-described clinical tests and the lab-based study.

Training:

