Patients will be assigned a study number, which will be used for all documentation except for a master list matching subjects names and study numbers, and forms for which subjects' names must be recorded (e.g. intake interview forms, copies of reimbursement receipts etc). The master list and interview forms will be kept in a secure location in locked offices. No non-study staff will have access to any identifiable patient study data or demographic information. All subjects' parents will be informed of their privacy rights and sign a HIPAA-compliant authorization form previously approved by the Spaulding IRB. Study staff in the Motion Analysis Laboratory will conduct quarterly audits to ensure compliance with regulatory standards for study documentation.

SENDING SPECIMENS/DATA TO RESEARCH COLLABORATORS OUTSIDE PARTNERS

Specimens or data collected by Partners investigators will be sent to research collaborators outside Partners, indicate to whom specimens/data will be sent, what information will be sent, and whether the specimens/data will contain identifiers that could be used by the outside collaborators to link the specimens/data to individual subjects.

No personally identifiable data will be sent to or viewed by collaborators outside of SRH.

Specifically address whether specimens/data will be stored at collaborating sites outside Partners for future use not described in the protocol. Include whether subjects can withdraw their specimens/data, and how they would do so. When appropriate, submit documentation of IRB approval from the recipient institution.

Data will not be stored for future use not described in the protocol.

RECEIVING SPECIMENS/DATA FROM RESEARCH COLLABORATORS OUTSIDE PARTNERS

When specimens or data collected by research collaborators outside Partners will be sent to Partners investigators, indicate from where the specimens/data will be obtained and whether the specimens/data will contain identifiers that could be used by Partners investigators to link the specimens/data to individual subjects. When appropriate, submit documentation of IRB approval and a copy of the IRB-approved consent form from the institution where the specimens/data were collected.

This study does not involve receiving data or specimens from outside collaborators.

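### Does expressing synergy change as a percentage of the full 0-1 cosine scale understate it, given that unrelated synergies already score well above 0?

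*SAP*

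**What the plan says.** The SAP's single analysis section, DATA ANALYSIS PLAN, defines the synergy score: "Cosine similarity values will be derived by comparing the composition of the muscle synergies pre- and post-intervention with normative synergies". It then defines the change: "The difference between post- and pre-intervention cosine similarity values will be measured as percentage of the scale (0-1 value"). For GMFM sections D and E it also uses a share of scale width: "the difference will be measured as percentage of the scale range (i.e. 39 points for the section D score and 72 points" for section E). The 10-meter walk, the 6-minute walk and the Edinburgh gait score are instead expressed relative to each child's baseline. The section opens by planning descriptive statistics for all primary and secondary outcomes and a before/after comparison of their values. It closes with the mean and SD of each change.

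The Protocol (RESEARCH DESIGN AND METHODS) plans "A convenience sample of 30 children with CP with no major orthopedic or neurological complications". Under Visit 1: Lab-based study it follows "guidelines to place up to 16 electrodes on several muscles involved in the gait pattern". In the text available for review, neither document states the factorisation method, the number of synergies, how they are matched to the normative set, or how many muscles enter the analysis.

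**The concern.** A cosine normally runs from -1 to 1. The SAP's 0-1 scale therefore implies non-negative weights. With such weights the cosine is 0 only when two synergies share no active muscle, so two unrelated synergies usually score well above 0. Pairing each one with its closest counterpart raises the score further. If that chance level is taken as the real bottom of the scale, the change has less than 1.0 to move in, and a percentage of 1.0 looks too small.

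The GMFM percentages in the next sentence sharpen the worry, because a reader might take 5% of the cosine scale and 5% of GMFM section D as equal shares of attainable change. The top end looks open as well. Only children with CP are recruited, and the Protocol section on receiving outside data says "This study does not involve receiving data or specimens from outside collaborators", so no typically developing children are on hand to show what a normal score is. A real reorganisation of synergies could then be read as negligible.

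**Working it through.** **Inputs.** From the SAP: scale width 1 for the cosine, 39 and 72 points for GMFM D and E. From the Protocol: up to 16 electrodes and 30 children. Assumed, because the documents are silent: non-negative weights (inferred from the 0-1 scale), 8 to 16 muscles, the weight distribution, the synergy count and the matching rule. The plan gives no chance level or expected cosine to reproduce.

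**1. What the SAP's unit is.** Percentage = 100 × (post − pre) / 1. A raw change of 0.05 gives 100 × 0.05 / 1 = 5%. The raw mean change in cosine units is therefore the planned figure divided by 100.

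**2. Whether 0-1 is the right range.** For non-negative vectors a and b, cosine = Σab / (‖a‖‖b‖). It is 1 when they are proportional and 0 when they share no active muscle. In simulated single pairs with about 30% of muscles active, the cosine was exactly 0 in 24% of pairs with 8 muscles and 12% with 16. Both ends are attainable.

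**3. Where unrelated synergies score on average.** Simulated means, with 8 / 16 muscles:

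| Assumed weights | No matching | One-to-one, 4 synergies | Best match with replacement, 4 synergies |
|---|---|---|---|
| Uniform | 0.761 / 0.756 | 0.832 / 0.805 | 0.860 / 0.826 |
| Exponential | 0.589 / 0.546 | 0.712 / 0.642 | 0.759 / 0.678 |
| About 30% active | 0.301 / 0.259 | 0.510 / 0.416 | 0.591 / 0.471 |
| One muscle per synergy | 0.125 / 0.0625 | not run | not run |

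Across all settings tried, chance ran from about 0.06 to 0.88. The figure follows from the assumptions, not from the documents.

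**4. The alternative scale.** Dividing by (1 − chance) instead of 1 multiplies the result by 1 / (1 − chance):
- chance 0.29: 1 / 0.71 = 1.41, so 5% becomes 7.0%;
- chance 0.86: 1 / 0.14 = 7.14, so 5% becomes 35.7%;
- the full range 0.06 to 0.88 gives factors of about 1.07 to 8.

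The arithmetic is right, but it compares two definitions. It does not show an error in the SAP's definition.

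**5. Whether chance is a floor.** It is the mean score of unrelated draws, so scores fall on both sides of it. With exponential weights and 8 muscles, single pairs averaged 0.584 and their 5th to 95th percentiles were 0.283 to 0.866. With 4 normative and 3 or 4 child synergies under one-to-one matching, 46% to 58% of unrelated sets scored below the chance mean.

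**6. Effect on inference.** In 30 simulated differences the mean was 0.0796 and the SD 0.1233, so mean/SD = 0.646 and t = 3.54. Rescaled with chance 0.86, the mean was 0.5688 and the SD 0.8808, and mean/SD and t were unchanged.

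**7. The GMFM comparison.** 5% is 0.05 × 39 = 1.95 points on section D and 0.05 × 72 = 3.6 points on section E. The SAP nowhere says these percentages are interchangeable with the cosine percentage. Three further outcomes use percentage of baseline, so no common unit is intended.

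**The case for a change.** The strongest case is about reading the result. The 0-1 scale itself points to non-negative weights, so the premise is close to the text. In a grid of 120 combinations of weights, muscle counts, synergy counts and matching rules, chance ran from 0.29 to 0.86 (median 0.66, median factor 2.9) and was nowhere near 0. In an illustration where two merged synergies fully separate in every child, with one-to-one matching, the reported mean change had a median of only 4.9 points, against 15.3% of the chance-to-1 range. The analysis is descriptive, so the size of the number is the result, and unchanged tests are little comfort.

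Part of this stands: cosines of non-negative vectors are often high even for unrelated synergies, and a reference from shuffled weights would help a reader. It does not make the planned figure wrong. The grid medians average over arbitrary settings and estimate nothing about this trial, and the illustration depends on its assumed change. The opening of the SAP section, on a natural reading, already covers the cosine values before and after training, which show where on the scale the change lies. A chance-corrected denominator would be estimated from the data, would depend on the matching rule, and would treat muscles as exchangeable. Statisticians could reasonably decline it.

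The Protocol notes that "Children with CP utilize fewer synergies during gait than typically developing children", so the synergy count could matter. Under unrelated weights, extracting 4 instead of 3 moved the score by anything from -3.3 to +19.7 points, depending on the matching rule. That comes from the unstated count and matching rule, not from dividing by 1. Likewise, the statement about outside collaborators does not rule out a published normative set or the laboratory's own, and the change can be computed without a typical child's score as upper limit.

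**Conclusion.** The concern does not hold. The planned percentage is 100 times the raw cosine change on a range whose two ends are attainable when weights are non-negative, so it understates nothing. The factor of 1.4 to 7 measures the distance to another scale that the SAP never adopts. It rests on assumptions outside the documents and widens to about 1.07 to 8 under other plausible ones. With a common chance level, direction, standardised change and any paired test are unaffected. Showing a chance reference beside the result is a reporting preference. The unstated synergy count, matching rule and normative source are separate matters of detail and do not make the 0-1 denominator an error.
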